1.3.4 Description of the drugs and devices to be studied

Doxycycline is almost completely absorbed with a bioavailability of >80%, and is only minimally affected by the presence of food in the gut.¹⁵ The half-life of absorption is 0.85±0.41 h. Serum levels are detectable within 15 minutes and peak serum concentrations are reached 2-3 hours after oral administration.^{15,16} Doxycycline levels within the endometrium are reached almost immediately.¹⁶ The elimination half-life is between 12 and 25 hours.¹⁵ A 2009 study showed that administering doxycycline with dinner the night before dilation and evacuation resulted in less emesis but lower serum concentration.³ There was no difference in serum concentration in patients with emesis compared to patients without emesis.³

Azithromycin has lower bioavailability than doxycycline (37%). Peak serum concentrations are reached 2-3 hours after oral administration. Azithromycin exits the serum rapidly and has tissue concentrations 10 to 100 times higher than serum concentrations.¹⁷ The estimated tissue half-life is greater than 60 hours for a single 500-mg dose, though the peak serum concentration is reached in 2-3 hours.¹⁷ While gastrointestinal side effects are the most common side effects, azithromycin is associated with significantly less nausea and emesis than erythromycin in pregnant patients.^{7,18}

Metronidazole has excellent bioavailability (>90%). Peak serum concentrations are reached 0.25-4 hours after oral administration of 500 mg.¹⁹ Tissue penetration in pelvic organs is approximately 90% of serum concentration, and half-life is 6-10 hours.¹⁹ Side effects are also primarily gastrointestinal, with 1.8% of 167 women in one study experiencing emesis.⁸

	Bioavailability	Time to peak serum concentration	Half-life
Doxycycline	>80%	2-3 hours	12-25 hours
Azithromycin	37%	2-3 hours	>60 hours (500 mg dose)
Metronidazole	>90%	0.25-4 hours (500 mg dose)	6-10 hours

1.3.5 Admission Procedure

After informed consent has been obtained and eligibility confirmed, the participant will complete a baseline survey of demographic, medical history, and baseline symptoms, notably nausea (Appendix C). If the participant is interested in the substudy, a second consent will be signed for the substudy. She will then be assigned the next of the sequentially numbered randomization packet. At the time of pre-medication with ibuprofen and other standard medications, the participant will take the study drug from the first envelope with water approximately 30-60 minutes prior to procedure (15-90 minutes acceptable range). Time of administration will be recorded on the patient's chart. All other medications given concurrently will be recorded. At PPMW and WHC, patients are typically given ibuprofen 800 mg, tramadol 50 mg, alprazolam 0.25 mg, and promethazine 25 mg. While we plan to use this for all study participants, medications will be tailored to the need of each woman, such as, for example, allergies to medications.

1.3.6 Follow-up Procedure

Immediately prior to procedure (acceptable range 0-15 minutes) the participant will complete a questionnaire (Appendix D) assessing the primary study outcomes. Time of questionnaire completion will be recorded on the patient's chart and on the questionnaire itself. The abortion procedure will be performed in the usual fashion at that facility. The details of the paracervical block will be recorded by the abortion provider: volume, local anesthetic concentration, and other agents added. Episodes of emesis during the procedure will be recorded by the provider.

For the patients enrolled in the substudy, immediately after completion of the uterine aspiration but before removal of tenaculum, the endometrial sample will be collected. The external os will be cleaned with chlorhexidine. The physician investigator will pass the endometrial sampling device to the fundus and then withdraw the plunger to collect a sample at the fundus. If a second pass is needed to collect an adequate sample, a new sterile device will be used. The sample will be placed in appropriate medium for anaerobic and aerobic culture.

After completion of the procedure, substudy patients will have a blood sample collected via venipuncture before leaving the procedure room. This sample will be spun and frozen until the end of the study. After unblinding of the study data, the serum for each participant will be sent for the appropriate assay to determine the level of doxycycline, azithromycin, or metronidazole, as appropriate. No testing will be performed for participants receiving placebo.

Prior to discharge from the recovery room, the participant will complete a final questionnaire in the recovery area, again assessing the study outcomes (Appendix E). After completing the final questionnaire, the second envelope will be opened. Participants receiving placebo will be given azithromycin 1 g. If azithromycin is contraindicated, doxycycline 100 mg twice daily for 3 days will be given. Then participants will be given a \$50 gift card. Participants in the substudy will be given an additional \$50, for

\$100 in total.

Each participant will also receive a telephone call 1-2 weeks after the abortion procedure to assess for evidence of infection (Appendix F). Date and time of completion of all questionnaires will be recorded.

1.3.7 Criteria for Discontinuation

Any participant who meets the following criteria after enrollment will be discontinued from the study: (1) decline further participation in the study, (2) receives IV sedation, or (3) decides not to proceed with surgical abortion.

For the substudy, (1) inability to confirm uterine evacuation, or (2) surgical complication that would make the endometrial assessment an unacceptable risk would disqualify a patient from continuing to participate in the study. Any patient disqualified from the substudy will continue in the main study.

1.3.8 Laboratory and Other Investigations

Endometrial samples will be sent to the University of Pittsburgh laboratory for processing. Serum sample will be sent to the appropriate commercial lab to perform the assays for doxycycline, azithromycin, or metronidazole, as appropriate. Serum placebo from participant receiving placebo will be discarded once the data is unblinded.

1.3.9 Data Management

Source documents will be stored in a locked room at the Medstar Research Institute. The study personnel who will be collecting and entering the data have extensive experience working with confidential medical information and will follow standard institutional procedures for data handling, verification, cleaning, and storage.

Data will be entered by study staff into a database and accessible only by the primary, co-investigators, and research coordinator via password protection. All source documents are maintained in locked files in a locked room. Appropriate firewall and virus scanning software are installed and updated routinely by the hospital support staff.

1.3.10 Data Analysis

Data analysis will be conducted using Stata. The baseline characteristics of the populations will be described. Primary outcomes will be recorded as described above in 1.1.2, 1.3.1, and 1.3.5. Outcomes will be assessed using parametric or non-parametric analysis as appropriate.

The primary analysis will be based on intention-to-treat analysis, as participants will be analyzed based on the randomization group they are assigned regardless of actual treatment. Although study discontinuation after enrollment is possible, we expect extremely low discontinuation in this one-day study.

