Protocol: A randomized controlled trial of three prophylactic antibiotic regimens for first trimester surgical abortion

NCT02756403

June 26, 2015

A randomized controlled trial of three prophylactic antibiotic regimens for first trimester surgical abortion

Fellow: [name]

Primary Mentor: [name] MPH

Additional Mentors: [name] MPH; [name] MPH

Fellowship Site: Washington Medstar Hospital

Date of initial proposal submission: January 2015

PROJECT SUMMARY

Justification for the project

Preoperative oral antibiotics have been shown to decrease infection rates for surgical abortion, and are universally recommended by the Society of Family Planning ¹. While data shows that that several different drug regimens appear to be effective in preventing perioperative infection,² we do not currently have data comparing side effects and patient tolerability of these various regimens. Data does suggest higher rates of nausea with doxycycline versus placebo,³ but we lack sufficient evidence to recommend any one medication over another. Azithromycin 500 mg, doxycycline 200 mg, and metronidazole 500 mg are recommended for use before abortion by Planned Parenthood and the National Abortion Federation, and have been widely adopted since the previously most commonly used regimen (doxycycline 200 mg twice daily for 7 days post-procedure) became unreasonably expensive. Prior to doxycycline price increase, the standard of care had been post-procedure prophylaxis.

Proposed research

This double-blinded randomized controlled trial will consist of 180 participants undergoing first-trimester surgical abortion. Each subject will be randomized to one of four groups:

1. Azithromycin 500 mg – single dose
2. Doxycycline 200 mg – single dose
3. Metronidazole 500 mg – single dose
4. Placebo (with post-procedure antibiotics: azithromycin 1 g once or doxycycline 200 mg twice daily for 7 days)

The primary outcomes are nausea, vomiting, and pain. Subjects will be assessed for the presence of these symptoms before administration of study drug, immediately following the abortion procedure, and again in the recovery area.

A substudy will assess for serum drug levels and for the presence of viable bacteria within the endometrial cavity in 40 women.

New features

This will be the first study to compare side effect profile and patient tolerability for the three most commonly used prophylactic antibiotic regimens for first-trimester surgical abortion.

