1.3 Design and Methodology

1.3.1 Research Design and General Methodological Approach

Primary study: We have designed a randomized controlled trial to be conducted at Washington Hospital Center (WHC) and Planned Parenthood of Metropolitan Washington (PPMW) over the course of 6-8 months. A total of 180 English-speaking women will be enrolled with 45 participants in each of the four groups.

The women will be randomized to receive single oral doses of azithromycin 500 mg, doxycycline 200 mg, metronidazole 500 mg, or placebo. Computer-generated randomization will be used to assign participants to one of the four treatment arms. Women receiving placebo will receive antibiotic prophylaxis after completion of the study.

Both the participants and the investigators will be blinded as to the treatment group. This will be accomplished by placing the study medication inside opaque gelatin capsules, a method that has been successful in prior studies.³ We will randomize participants by assigning them to the next of the sequentially numbered sealed opaque study packets, containing the gelatin capsules with study medication inside. A second smaller opaque sealed envelope will also be inside the study packet. This envelope will be opened after completion of all study procedure and will only say if the participant received placebo, so that additional antibiotics can be given.

Participants will swallow the appropriate medication approximately 30-60 minutes prior to the surgical abortion. We will assess side effects via written questionnaire immediately before the start of the procedure and in the recovery room. Study population will be all eligible patients undergoing surgical abortion in the first trimester at PPMW and at WHC.

For the substudy 40 women will be recruited to undergo immediate post-procedure endometrial sampling using a suction-piston device. Due to the double-blind nature of this study, enrollment into the substudy will not be by group. Thus there are likely to be unequal group sizes. For a pilot substudy such as this, unequal numbers within groups will not detract from the utility of the results.

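### Nausea is recorded before dosing, but the analysis plan does not use it to adjust the primary nausea comparison; prespecifying that adjustment is a nearly free gain in precision

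*Combined protocol and SAP*

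**What the plan says.** Nausea is a primary outcome in both the Project Summary and section 1.1.2. Section 1.3.5 has it measured before the randomisation packet is assigned: "the participant will complete a baseline survey of demographic, medical history, and baseline symptoms, notably nausea (Appendix C").

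Section 1.3.10 gives baseline data one use: "The baseline characteristics of the populations will be described". On the outcomes it says "Primary outcomes will be recorded as described above in 1.1.2, 1.3.1, and 1.3.5" and then "Outcomes will be assessed using parametric or non-parametric analysis as appropriate". The cross-reference includes 1.3.5, the baseline survey, but not 1.3.6, where the post-dose questionnaires are set out.

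The post-dose assessment times differ between sections:

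- Project Summary: symptoms are "assessed for the presence of these symptoms before administration of study drug, immediately following the abortion procedure, and again in the recovery area".
- Section 1.3.1: "We will assess side effects via written questionnaire immediately before the start of the procedure and in the recovery room".
- Section 1.3.6: "Immediately prior to procedure (acceptable range 0-15 minutes) the participant will complete a questionnaire (Appendix D) assessing the primary study outcomes"; later, "the participant will complete a final questionnaire in the recovery area, again assessing the study outcomes (Appendix E").

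Section 1.3.11 sizes the trial at 45 per group for a 30% difference from placebo, with 80% power and alpha 0.05.

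**The concern.** A pre-dose measure of a primary outcome is usually among the better available predictors of its post-dose value. Adjusting for it removes between-woman variation from the treatment comparison without any new data. The plan collects the measure and gives it no stated role in the comparison.

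What is at stake is precision, not bias. Each drug has only 45 women to set against 45 on placebo, so a few points of power are worth having when they cost nothing. The open wording also leaves the method to be chosen later. It would allow an unadjusted change from baseline, which can be less precise than ignoring baseline altogether. Finally, no adjusted comparison can be specified until one post-dose time point is fixed, and the sections disagree on which time points exist.

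**Working it through.** **Inputs from the documents.** 45 per arm, alpha 0.05, 80% power and a 30% difference from placebo (1.3.11); equal allocation to four arms (1.3.1); nausea measured before dosing (1.3.5). Two-sided testing is assumed. The documents give no nausea rate, baseline prevalence, baseline-to-outcome association or scale, so every such value below is an assumption, shown over a range.

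**1. Reproducing 45 per group.** Read 30% as an absolute difference between two proportions, with mean rate p̄:

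n = [1.96·√(2p̄(1−p̄)) + 0.842·√(p₁(1−p₁)+p₂(1−p₂))]² / (p₂−p₁)²

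The continuity-corrected size is n_c = (n/4)·[1 + √(1 + 4/(n·|p₂−p₁|))]².

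For 20% vs 50%: n = (1.322 + 0.539)²/0.09 = 38.5 and n_c = 44.9, which rounds up to 45. For 10% vs 40%, n_c = 37.9; for 30% vs 60%, n_c = 48.4. The plan's figure therefore fits a yes/no outcome with a placebo rate near 20%. Without the continuity correction, power at 45 per arm for 20% vs 50% is 86%, which is the reference value in step 2.

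**2. Yes/no nausea.** Simulation of 40,000 drug-versus-placebo trials per scenario, comparing a Mantel-Haenszel test stratified by baseline nausea with the same test unstratified. Placebo/drug rates were 10/40, 20/50 and 30/60%. Baseline prevalence was 20, 30, 40 and 50%. The odds ratio links baseline to post-dose nausea.

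| Baseline odds ratio | Change in power (points) |
|---|---|
| 1 | −0.2 to +0.5 |
| 2 | +0.1 to +1.8 |
| 3 | +0.8 to +3.2 |
| 5 | +1.9 to +5.9 |
| 10 | +3.3 to +9.4 |

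At 20% vs 50% and odds ratio 3, power goes from 86% to 87–88%. An odds ratio of 10 is extreme: with 40% baseline prevalence and a 20% placebo rate, it means 6% vs 40% post-dose nausea on placebo according to baseline status. With no drug effect, rejection rates were 4.4–5.2% unstratified and 4.8–5.2% stratified, so the small apparent gain at odds ratio 1 reflects discreteness of the unstratified test.

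Two other ways of adjusting agree:

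- Risk-difference regression with robust standard errors (20% vs 50%, prevalence 20% and 40%): −0.9 to −0.8 points at odds ratio 1, −0.3 to +0.3 at 2, and +0.4 to +1.4 at 3.
- Logistic regression with a standardised risk difference: about −0.6 at odds ratio 1, +1 at 3 and +3 at 5.

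**3. Nausea as a score.** Take the standardised difference that 45 per arm detects with 80% power, so that the noncentrality is 1.960 + 0.842 = 2.802. Analysis of covariance multiplies the variance by 1−ρ², where ρ is the correlation of baseline with outcome:

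Power = Φ(2.802/√(1−ρ²) − 1.96) = 80.0, 81.6, 83.6 and 89.9% at ρ = 0, 0.2, 0.3 and 0.5.

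**4. Unadjusted change score.** With k = baseline SD / post-dose SD:

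Power = Φ(2.802/√(1+k²−2kρ) − 1.96)

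This beats no adjustment only when ρ > k/2.

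| k | Break-even ρ | ρ = 0 | ρ = 0.3 | ρ = 0.5 |
|---|---|---|---|---|
| 0.5 | 0.25 | 71% | 82% | 90% |
| 0.75 | 0.375 | 61% | 76% | 87% |
| 1 | 0.5 | 51% | 66% | 80% |

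**5. Time points.** The Project Summary has one assessment immediately after the procedure and one in recovery. Sections 1.3.1 and 1.3.6 have one immediately before the procedure and one in recovery. Recovery (Appendix E) is the only post-dose point in all three, and section 1.3.2 counts the 180 completers on that questionnaire.

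**The case against.** The strongest reply is that nothing here is wrong. An unadjusted comparison is unbiased under randomisation and keeps the designed power, and covariate adjustment is optional. Section 1.3.10 specifies no model, so it does not exclude a baseline term. Its reference to 1.3.5 could even be read as giving the pre-dose value some role. All of this stands, and it limits the point to one of prespecification and efficiency.

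The gain may also be small. On the yes/no reading, which the Project Summary's wording about presence of symptoms and the fit of 45 per group both favour, it is at most 1.8 points at an odds ratio of 2 and 3.2 at 3. Excluding women too nauseated for oral intake (1.3.2) and giving promethazine alongside the study drug (1.3.5) may weaken the association. So may the longer interval to the recovery assessment. This stands too, and it is why the gain is given as a range.

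Three lesser points have some force. Appendices C to E are listed but not available here, so the scale may be defined on the forms; what can be said is that the analysis section names none. Section 1.3.6 describes Appendix D as assessing the primary outcomes, so agreement across sections on Appendix E does not settle which time point is scientifically best. And the plan never proposes a change score, so step 4 is a caution about what the wording leaves open.

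None of this removes the case for adjusting. The measure is already collected, the loss if it proves uninformative is under 1 point, and the likely gain is as large or larger.

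**Conclusion.** The point holds and is minor. The plan collects pre-dose nausea and does not prespecify its use in the primary nausea comparison. The validity of the trial is not in question.

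The gain is modest for yes/no nausea: roughly 1 to 3 points of power at a baseline odds ratio of 3, and about 2 to 6 at 5. For a score it is about 2 to 10 points at correlations of 0.2 to 0.5. The worst case for the adjusted methods examined is a loss of under 1 point. These sizes rest on assumed nausea rates, baseline prevalence and association, and on two-sided testing with 45 per arm. Confidence in the size is medium because the documents give none of those inputs except the number per arm.

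**What to change.** Amend section 1.3.10 before unblinding:

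1. Reconcile the assessment times in the Project Summary with those in 1.3.1 and 1.3.6, and name one primary post-dose nausea time point. The recovery questionnaire (Appendix E) is the only one all three share. Add 1.3.6 to the cross-references in 1.3.10.
2. State whether nausea is analysed as yes/no or as a score.
3. State that each drug-versus-placebo comparison is adjusted for the Appendix C nausea measure. For yes/no nausea, use a Mantel-Haenszel analysis stratified by baseline nausea, or logistic regression reported as a standardised risk difference, which stays on the absolute-difference scale that 45 per group fits. For a score, use analysis of covariance, in a rank-based or robust form if the data are skewed. Neither requires Appendix C to use the same scale as D or E. The covariate must be the Appendix C value, because Appendix D is completed after dosing.
4. Rule out an unadjusted change score, and report the unadjusted comparison as supportive.

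The cost is two or three sentences in 1.3.10, plus the wording needed to align the assessment times elsewhere. No new data, visits or participants are required.

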1.3.11 Number of Subjects and Statistical Power

Sample size: 180 women for main study

To detect a 30% difference in a given outcome compared to the placebo group, we will need to enroll 45 women per group to achieve a power of 80% with alpha of 0.05.

For the endometrial sampling substudy, we will enroll 40 women. As this has not been done previously,

we cannot predict results with any accuracy. We expect that roughly 10 women per group will give us enough data to understand if this methodology will be fruitful for future research, without undue risk to a large number of women at this early stage. Enrollment in the sub-study may be more challenging but we need many fewer participants. To give a rough idea of power, the substudy will have 85% power with alpha of 0.05 to detect a reduction in positive culture (any bacteria detected) from 90% with placebo to 20% in a treatment group. This assumes 10 women per group.

1.3.12 Study Limitations

A study of this size will only be able to examine common outcomes such as emesis and nausea. A much larger study would be needed to look at outcomes such as adverse drug reactions or post-abortion infection.

Patients will be recruited from WHC and PPMW. While they are representative of women in this area, they may not be generalizable to women with different characteristics.

The use of the smaller envelope to be opened after completion of the study creates some risk that blinding will be lost. However, we feel that this risk is minimal. This method is the simplest solution for women receiving placebo antibiotics after the abortion.

1.3.13 Duration of Project

Recruitment is expected to begin in July 2015 and continue until 180 participants have completed the study. Based on surgical volumes and prior experience, this should be achievable within 6-8 months. Recruitment of subjects, data collection, follow-up of subjects (with the exception of the 1-2 week telephone call) and data entry will be completed on the same day of the initial consultation for the procedure. For a similar one-day study of second-trimester cervical preparation, we easily recruit 2-4 participants per week at PPMW on Thursdays, our maximum per day to avoid disrupting clinic flow. Since this proposed study is simpler, we anticipate enrolling 4-6 participants per day at PPMW with the option to enroll 2 days per week. At WHC, we expect to enroll 2-6 women per week at WHC, from the roughly 10-20 first-trimester procedures per week. Thus we feel that we can safely estimate enrolling 10-15 women per week. At 10 women per week, we would need 18 weeks or 4-5 months. However since delays seem inevitable, we estimate 6-8 months for enrollment.

Data analysis will follow and be completed prior to writing the final paper. Please see the timeline for graphical depiction.

